4.5.5.11 EuroQOL 5-Dimension Questionnaire

The EuroQOL 5-Dimension questionnaire (EQ-5D) is a standardized measure of health status designed to provide a simple generic measure of health for clinical and economic appraisal. It is broadly applicable across a wide range of health conditions and treatment.

The EQ-5D assesses five domains to provide a health state index. These are anxiety/depression, pain/discomfort, usual activities, mobility, and self-care.

Two versions are used in this study: EQ-5D 5-Level (EQ-5D-5L) proxy Version 1, reported on behalf of the patient, and the EQ-5D-5L patient version provided to caregivers to assess caregiver health status.

4.5.6 Electronic Assessment of Rating Scales

The following rating scales will be captured electronically and transferred to the database directly from the core laboratory: ADAS-Cog, ADCS-ADL, CDR, C-SSRS, *EQ-5D-5L*, FAQ, FCSRT, MMSE, NPI-Q, QoL-AD, and ZCI-AD.

4.5.7 Laboratory, Biomarker, PK and Other Biologic Samples

4.5.7.1 Standard Laboratory Samples

Samples for the following laboratory tests will be sent to a central laboratory for analysis. Instruction manuals and supply kits will be provided for all central laboratory assessments. For sampling procedures, storage conditions, and shipment instructions, see the Sample Handling and Logistics Manual.

- Serum chemistry: AST, ALT, ALP, total protein, total bilirubin, serum albumin, CPK, sodium, potassium, calcium, BUN or urea, and serum creatinine (and creatinine clearance calculated by the central laboratory)

- Hematology: hemoglobin, hematocrit, RBC (with morphology), WBC counts, platelet, basophil, eosinophil, lymphocyte, monocyte, neutrophil, and WBC (other total counts)
- Coagulation: PT (pre-first infusion)
- Immunophenotyping, including CD4, CD8, CD3, CD19, CD16+56
- Urinalysis will be performed at the site by dipstick for blood, protein, glucose, and pH. Microscopic examination will be performed at the central laboratory if blood and/or protein results are positive or strongly positive. Results do not need to be recorded on the eCRF.
- Urine for pregnancy

Urine pregnancy testing will be performed at each dosing visit for women of childbearing potential (including those who have had a tubal ligation), and at the site for any other female participants if required by local regulations. If a urine pregnancy test is positive, it must be confirmed by a serum pregnancy test at the central laboratory.

4.5.7.2 Cerebrospinal Fluid Sampling

This section applies for patients who took part in the substudy associated with Study BN29552 or BN29553 and have opted to allow a further CSF sample to be taken during the OLE study. CSF samples will be collected *in the OLE study at Week 53 or at the early termination visit if prior to Week 53 and at least 6 months have elapsed since the previous lumbar puncture* (see [Appendix 1](#)).

Lumbar puncture will be performed by an individual who meets all local requirements and is proficient in the procedure. Lumbar puncture procedures and post-lumbar puncture care will be performed in accordance with local practice. CSF sampling should be performed in the morning (between 8:00 a.m. and noon) to minimize potential diurnal variation of CSF parameters.

Approximately 12 mL of CSF will be collected from patients.

The samples will be used to study the effect of crenezumab on biomarkers associated with AD; for research purposes to identify biomarkers that may be predictive of response to treatment with crenezumab; to better understand the pathogenesis, course, and outcome of AD and related diseases; and to support the development of biomarker assays for diagnostic use.

CSF samples (i.e., biomarker samples) will be destroyed no later than 5 years after the final Clinical Study Report has been completed. However, the storage period will be in accordance with the IRB/EC-approved Informed Consent Form and applicable laws (e.g., health authority requirements). For patients who consent to the optional Research Biosample Repository (RBR), residual biomarker samples may be kept longer for future biomarker research (see Section [4.5.10](#)).

The procedures for the collection, handling, and shipping of biomarker samples are specified in the Sample Handling and Logistics Manual.

4.5.7.3 Plasma Biomarker Sampling

Plasma sampling will be conducted at Week 53 of the OLE study *or at the early termination visit if prior to Week 53* only as detailed in the schedule of activities (see [Appendix 1](#)). One whole blood sample will be obtained for plasma extraction from all patients.

This sample will be used to evaluate plasma A β levels in peripheral blood as PD markers and to evaluate other exploratory AD biomarkers.

Plasma samples (i.e., biomarker samples) will be destroyed no later than 5 years after the final Clinical Study Report has been completed. However, the storage period will be in accordance with the IRB/EC-approved Informed Consent Form and applicable laws (e.g., health authority requirements). For patients who consent to the optional RBR samples, residual biomarker samples may be kept longer for future biomarker research (see Section [4.5.10](#)).

The procedures for the collection, handling, and shipping of biomarker samples are specified in the Sample Handling and Logistics Manual.

4.5.7.4 Amyloid- and Tau-PET Assessments

This section applies for patients who took part in either the amyloid- and/or tau-PET substudies associated with Study BN29552 or BN29553 and have opted to have a further amyloid- and/or tau-PET assessment during the OLE study.

The amyloid- and tau-PET assessments will allow longitudinal evaluation of the effect of crenezumab on cerebral fibrillar amyloid deposition as measured by florbetapir *F 18*-PET in this study population and tau burden as measured by [^{18}F]GTP1 (an investigational radioligand for in vivo imaging of tau protein aggregates).

The PET data collected are expected to help in understanding the effects of crenezumab on amyloid and tau pathology over time as well as the relationship between change in florbetapir *F 18*/[^{18}F]GTP1-PET and change in other endpoints in the Phase III studies and OLE study.

PET Imaging Procedures: For Amyloid-PET and Tau-PET Assessments

The Sponsor in conjunction with the CRO will prepare and distribute a detailed Imaging Manual for image acquisition and reconstruction procedures and parameters for each center prior to the start of the study. All imaging data will be transferred to the imaging CRO for quality control and image analysis as documented in the PET Imaging Charter.

Amyloid-PET Assessments

One further amyloid-PET scan is included in this OLE study. This assessment will be done at Week 53 of the OLE study or at the early termination visit *if prior to Week 53 and* at least 6 months have elapsed since the previous amyloid-PET scan (see [Appendix 1](#)) and annual radiation exposure limits as per local guidelines are not exceeded.

The selective amyloid-PET radioligand florbetapir *F 18* must be used for this assessment.

During the DBTP in Study BN29552 or BN29553, substudy patients will have had screening, treatment, and post-treatment imaging studies. With the addition of the amyloid scan during the OLE study, each patient may have received florbetapir *F 18* on four occasions over the course of 3 years (or less in case of early termination).

Detailed methodology, including scanning procedures, is included in the Imaging Manual.

Source of Production of Florbetapir *F 18*

Florbetapir *F 18* will be provided in accordance with approved national and/or local standards.

Warnings and Precautions Associated with Florbetapir *F 18* (AMYVID)

The most commonly reported adverse reactions after injection of florbetapir *F 18* are headache (2%), musculoskeletal pain (1%), fatigue (1%), and nausea (1%).

For more information, see the Amyvid (Florbetapir *F 18* Injection) for Intravenous Use U.S. Package Insert or Amyvid Summary of Product Characteristics.

Tau-PET Assessments

The selective tau-PET radioligand [¹⁸F]GTP1 will be used in this OLE study as an additional PET assessment to be done at Week 53 or the early termination visit *if prior to Week 53 and* at least 6 months have elapsed since the previous tau-PET scan (see [Appendix 1](#)), and annual radiation exposure limits as per local guidelines are not exceeded.

During the DBTPs of Study BN29552 and BN29553, patients received [¹⁸F]GTP1 and had tau-PET scans on up to three occasions (at baseline, Week 53, and Week 105 or the early termination visit). With the addition of the tau scan during the OLE study, each patient may have received [¹⁸F]GTP1 on four occasions over the course of 3 years (or less in case of early termination).

If occurring in the same visit, [¹⁸F]GTP1 PET scans will be performed after administration of clinical scales. [¹⁸F]GTP1 PET scans should not be performed on the same day as other PET scans.

Source of Production of [¹⁸F]GTP1

[¹⁸F]GTP1 will be provided under contract with a tau-PET imaging CRO in accordance with approved national and/or local standards.

Warnings and Precautions Associated with [¹⁸F]GTP1

[¹⁸F]GTP1 is not approved by any health authority, and clinical development is ongoing. The safety plan for participants in this study is based on clinical experience with [¹⁸F]GTP1 in *three* completed and *three* ongoing studies, and the safety experience to date is detailed in the [¹⁸F]GTP1 Investigator's Brochure.

4.5.7.5 Immunogenicity Sampling

Blood samples will be collected to assess the possible development of ADAs in all patients as noted in the schedule of activities (see [Appendix 1](#)). In addition, in case of anaphylaxis, anaphylactoid, or serious or severe hypersensitivity reactions, an ADA

sample with a concurrent serum PK sample should be collected at the time of the event and at washout (16 weeks) in the case of discontinuation for anaphylaxis. Serum samples will be analyzed for antibodies to crenezumab using a validated bridging ELISA. Samples may be tested for antibodies against other drug product substances.

The procedures for the collection, handling, and shipping of ADA samples are specified in the Sample Handling and Logistics Manual supplied to the site by the Sponsor.

4.5.7.6 Pharmacokinetic Sampling Serum Crenezumab

Blood samples will be collected to evaluate the pharmacokinetics of crenezumab in serum as noted in the schedule of activities (see [Appendix 1](#)). An additional PK sample for the assessment of serum concentrations of crenezumab may be obtained if the patient makes an unscheduled visit. Unscheduled PK samples should be taken in the event of anaphylaxis, anaphylactoid, or serious or severe hypersensitivity reactions and at washout (16 weeks) in the case of discontinuation for anaphylaxis.

Serum concentrations of crenezumab will be determined using validated analytical procedures.

4.5.8 Electrocardiograms

In all patients, a routine ECG monitoring approach will be used. Single ECG recordings will be obtained at specified timepoints, as outlined in the schedule of activities (see [Appendix 1](#)) and may be obtained at unscheduled timepoints as clinically indicated.

All ECG recordings must be performed using a standard high-quality, high-fidelity, digital electrocardiograph machine equipped with computer-based interval measurements. Lead placement should be as consistent as possible. ECG recordings must be performed after the patient has been resting in a supine position for at least 5 minutes. All ECGs are to be obtained prior to other procedures scheduled at that same time (e.g., *weight, pulse rate, systolic and diastolic blood pressure, respiratory rate, oxygen saturation, and body temperature*). Circumstances that may induce changes in heart rate, including environmental distractions (e.g., television, radio, conversation) should be avoided during the pre-ECG resting period and during ECG recording.

For safety monitoring purposes, the investigator must review, sign, and date all ECG tracings. Paper copies of ECG tracings will be kept as part of the patient's permanent study file at the site. Digital recordings will be analyzed at the central ECG laboratory and data transmitted to Roche.

The following should be recorded by the electrocardiograph machine: heart rate, respiratory rate interval, QRS interval, pulse rate duration, uncorrected QT interval, and QT interval corrected through use of Fridericia's formula (QTcF) and Bazett's formula based on the machine readings of the individual ECG tracings.

If the QTcF is >500 ms and/or >60 ms longer than the baseline value, another ECG must be recorded, ideally within the next 5 minutes, and ECG monitoring should continue until QTcF has stabilized on two successive ECGs. The Medical Monitor should be notified. Standard-of-care treatment may be instituted per the discretion of the investigator. If a PK sample is not scheduled for that timepoint, an unscheduled PK sample should be obtained. When 12-lead ECGs are scheduled at the same time as blood draws, the blood draws will be obtained at the scheduled timepoint, and the ECGs will be obtained prior to but as close to the scheduled blood draw as possible.

4.5.9 Brain Magnetic Resonance Imaging

The MRI should be performed using a scanner with a field strength of 1.5 T or higher and where practical, the same scanner should be used for an individual patient for the entire duration of the study.

MRI will be used during the study to help assess safety such as the occurrence of microbleeds or signs potentially indicative of inflammation or ARIA-E. Additional unscheduled MRI scans may be utilized to better understand relevant CNS-related adverse events (such as increased confusion) or to follow a sign that emerges at a scheduled scan; contrast agent may be used in such a case of follow-up if administration of contrast agent is considered safe for the patient according to local standards. Finally, MRI will be performed at multiple timepoints to determine potential treatment effects on various MRI outcome measures (see [Appendix 1](#)).

Patients who have a CSF sample taken at Week 53 should either undergo lumbar puncture for CSF sample and then wait for 3 days before having MRI or, ideally, undergo MRI before the CSF sample is taken.

During study conduct, within 3 days prior to the scheduled MRI visit, site staff should contact the patient or caregiver to prospectively determine whether the patient is experiencing any CNS-related symptoms. MRI results must be available for review by site staff before dosing can occur.

Details regarding image acquisition and data transfer by the scanning facilities, and the procedures, clinical assessments, and quantitative measurements performed by the core laboratory can be found in the MRI Charter and Scanning Manuals.

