- c Study drug administration should be performed only after all assessments/rating scales have been completed (unless indicated otherwise). Study drug will be administered to patients by infusion (full details in the pharmacy manual). Patients must be observed for a minimum of 1 hour after dosing and vitals should be assessed immediately after infusion is completed, and then ≥ 60 minutes post-infusion. There should be a telephone call to the patient following the first infusion.
- d Visit may be split over 2 days. All cognitive and functional assessments should be completed first. All safety assessments (e.g., visits, blood tests, and ECGs) should be completed on the day of dosing.
- e A final annual assessment (Week 53 or Week 105) will be obtained for patients who discontinue study treatment prior to Week 105. If the next annual visit (Week 53 or Week 105) is expected within 3 months of the discontinuation, the final annual visit may be combined with the 4-week postdose safety visit.
- f The coagulation test can be done *as soon as* the OLE main Informed Consent Form has been signed.
- g Vital signs include measurements of weight, pulse rate, systolic and diastolic blood pressure, respiratory rate, oxygen saturation, and body temperature. The same arm should be used for all blood pressure measurements. Pulse rate and blood pressure should not be measured unless 15 minutes have passed since the last blood draw. Vital sign assessments should be performed just prior to study drug administration, at the end of infusion, and 60–90 minutes after the end of infusion. All vital signs should be recorded in the eCRF.
- h Urinalysis will be performed at the site by dipstick for blood, protein, glucose, and pH. Microscopic examination should be performed at the central laboratory if blood and/or protein results are positive or strongly positive. Results do not need to be recorded on the eCRF.
- i Females of childbearing potential (including those who have had a tubal ligation) must have a urine pregnancy test performed at the site prior to each dose administration. If a urine pregnancy test is positive, it must be confirmed by a serum pregnancy test at the central laboratory. Results are to be recorded only in the source documents.

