- j Predose PK samples and plasma pharmacodynamics should be obtained prior to study drug administration on the same day of dosing. Accurate recording of the time of study drug administration and pharmacokinetics is critical. Unscheduled PK samples should be taken in the event of anaphylaxis, anaphylactoid, or serious or severe hypersensitivity reactions. For any patient suspected of developing anaphylaxis, or anaphylactoid or serious or severe hypersensitivity reactions warranting discontinuation of dosing, collect a wash-out ADA sample (16 weeks postdose) and concurrent PK sample.
- k An additional PK sample should be collected 60–90 minutes after end of infusion.
- l Immunogenicity samples should be obtained prior to study drug administration on the same day of dosing; samples should be taken to measure antibody development to crenezumab (ADAs) and other drug component products. Unscheduled samples should be taken in the event of anaphylaxis, anaphylactoid, or serious or severe hypersensitivity reactions at the time of the event. For any patient suspected of developing anaphylaxis, or anaphylactoid or serious or severe hypersensitivity reactions warranting discontinuation of dosing, collect a wash-out ADA sample (16 weeks postdose) and concurrent PK sample.

Appendix 1

Schedule of Activities: Open-Label Extension Study (cont.)

- ^m CSF PK and biomarker samples, amyloid-PET, and tau-PET should be taken for patients who were in the respective longitudinal substudies of Studies BN29552 or BN29553 and have *consented to additional sampling in the OLE*. Florbetapir F 18 must be used for the amyloid-PET assessment. The same scanner should be used as used in the substudy associated with Study BN29552 or BN29553. Any scanner changes must be approved by the Sponsor. See Section 4.5.7 for details of sampling. CSF samples should be collected prior to dosing at the same day of dosing or the day prior to dosing. It is critical that the actual date and the time of sample collection is recorded.
- ⁿ *Plasma PD, CSF, and/or PET assessment to be performed at Week 53. In the event that a patient terminates participation in the study prior to the Week 53 visit, the assessment should be performed at the early termination visit. CSF and/or PET assessments will not be performed at early termination if less than 6 months have elapsed since the previous CSF and/or PET assessment.*

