- ^o Perform after the patient has been in a supine position for 5 minutes. ECGs for each patient should be obtained from the same machine whenever possible and performed prior to any other assessments (e.g., weight, pulse rate, systolic and diastolic blood pressure, respiratory rate, oxygen saturation, and body temperature).
- ^p *Complete physical and neurologic examinations should include an evaluation of the head, eyes, ears, nose, and throat, and the cardiovascular, dermatologic, musculoskeletal, respiratory, gastrointestinal, and neurologic systems. Neurologic examinations should include assessment of mental status, level of consciousness, cranial nerve function (including fundoscopic examination), motor function, sensory function, reflexes, coordination, and assessment of gait. Other examination components or systems may be assessed as clinically indicated. Symptom-directed physical and neurologic examinations may be done at any other visit as needed to assess the safety of the participant.*
- ^q Serum chemistry includes AST, ALT, ALP, total protein, total bilirubin, serum albumin, CPK, sodium, potassium, calcium, BUN or urea, and serum creatinine (and creatinine clearance calculated by the central laboratory).
- ^r Hematology includes hemoglobin, hematocrit, RBC (with morphology), WBC counts, platelet, basophil, eosinophil, lymphocyte, monocyte, neutrophil, and WBC (other total counts). In the event of pneumonia, immunophenotyping analysis of peripheral blood cells should be done.
- ^s MRIs should be done at Weeks 13, 25, 53, 105, and yearly thereafter. MRI central read results must be available for review by site staff before dosing can proceed. The patient will be called in advance of the MRI to check for any CNS-related symptoms.
- ^t FAQ for *caregivers* of patients from Study BN29553.
- ^u Only study-related serious adverse events will be collected (see also Section 5.6).

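### At a Week 53 visit with dosing, the lumbar-puncture-first order allowed in Section 4.5.9 cannot be carried out together with the CSF predose window and the MRI-before-dosing rule

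*Combined protocol and SAP*

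**What the plan says.** Four rules in the current text bear on the Week 53 visit of a CSF-substudy patient.

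- **Order of procedures.** Section 4.5.9 offers two orders to patients with a Week 53 CSF sample. Under the first, they "should either undergo lumbar puncture for CSF sample and then wait for 3 days before having MRI". The second, which the section prefers, reverses the sequence: "or, ideally, undergo MRI before the CSF sample is taken".
- **MRI before dosing.** The next paragraph of Section 4.5.9 states that "MRI results must be available for review by site staff before dosing can occur". Appendix 1 footnote s repeats this for the central read: "MRI central read results must be available for review by site staff before dosing can proceed".
- **CSF window.** Appendix 1 footnote m: "CSF samples should be collected prior to dosing at the same day of dosing or the day prior to dosing".
- **Both fall at Week 53.** Footnote s: "MRIs should be done at Weeks 13, 25, 53, 105, and yearly thereafter". Footnote n: "Plasma PD, CSF, and/or PET assessment to be performed at Week 53".

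The schedule also has a serum PK sample at Week 53, which footnote j ties to the day of dosing, before the infusion. Section 6.5.3 plans to tabulate the ratio of CSF to serum crenezumab. Section 3.4.6 gives partitioning into the CSF at the 60 mg/kg dose as a purpose of the Week 53 CSF sample.

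**The concern.** Section 4.5.9 presents puncture first as an acceptable order and does not warn that it clashes with other rules. A site that follows it at a dosing visit appears bound to break one of two rules.

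- **If the CSF window gives way**, the CSF and the dosing-day serum sample are several days apart, and the planned ratio mixes two points on the concentration curve. This is the only scheduled CSF timepoint in the extension.
- **If the MRI rule gives way**, the infusion is given before the scan that is meant to clear it. Week 53 is the only scheduled MRI between Weeks 25 and 105.

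**Working it through.** The plan gives no figure to reproduce; this is a check on days. Let L be the day of lumbar puncture, M the day of MRI, D the day of dosing and r the central read time in days.

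**Constraints**

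1. Puncture first (Section 4.5.9): M ≥ L + 3. A stricter reading of the wait gives M ≥ L + 4.
2. MRI results before dosing (Section 4.5.9, footnote s): D ≥ M + r, with r ≥ 0.
3. CSF window (footnote m): D − L is 0 or 1.

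**Puncture first**

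Constraints 1 and 2 give D ≥ L + 3 + r, so D − L is at least 3. Constraint 3 needs D − L to be at most 1. No value of r satisfies both. Enumerating the days with D within ±7 of nominal Week 53 and r of 0, 1, 2, 3, 5 and 7 (an assumed range) gave no feasible schedule under either reading of the wait. The smallest puncture-to-dose gap was 3 days at r = 0, 4 at r = 1 and 10 at r = 7. The visit windows do not help, because the conflict lies in the spacing between the procedures and not in calendar position. Footnote d ("Visit may be split over 2 days") does not help either, since puncture and MRI alone are at least 3 days apart.

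If footnote m is kept instead, the latest permitted dose is D = L + 1 and the earliest MRI is L + 3, so the dose comes at least 2 days before the scan is taken.

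**MRI first**

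The constraints become M ≤ L, D ≥ M + r, and D − L of 0 or 1. Scanning on day D − r and puncturing on day D before the infusion satisfies all three for any r. With MRI and dose both within ±7 days, the enumeration found 225 feasible combinations at r = 0 and 72 at r = 7.

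**Size of the PK mismatch if the MRI rule is kept**

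Section 1.2.5 gives a terminal half-life of 17–26 days after single IV doses in Study ABE4427g. Over t days serum falls by the factor 2^(t / half-life):

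| Gap t (days) | Half-life 26 days | Half-life 17 days |
|---|---|---|
| 1 (most that footnote m allows) | 1.03 | 1.04 |
| 3 (minimum, r = 0) | 1.08 | 1.13 |
| 4 (r = 1, assumed) | 1.11 | 1.18 |
| 7 (r = 4, assumed) | 1.21 | 1.33 |

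Only the 3-day row is free of an assumed read time. These factors describe serum alone. Compared with a ratio from CSF and serum drawn together at the puncture, using the later serum sample inflates the ratio by this factor. Compared with a trough ratio on the dosing day, the distortion depends on how CSF concentration moves over the gap: the same factor if CSF falls in parallel with serum, and none if CSF stays flat.

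**The case against.** The strongest reply is that no site is forced into a breach. The sentence that offers puncture first also offers, and prefers, MRI first, and that order meets both footnotes. This stands. A reader might infer that any site in the CSF substudy must break a rule at Week 53; the documents do not support that. Only sites that choose puncture first are affected. At an early termination visit, or while study drug is interrupted, there is no dose and so no conflict.

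A reader might also infer that patients are as likely to be dosed without an MRI read as to have mistimed CSF. The wording points the other way: the MRI rule is a must, stated twice, and footnote m is a should. CSF timing is the rule more likely to give way.

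Third, one could attach a larger bias to the ratio, such as the 11% to 33% in the 4- and 7-day rows. That needs a read time of 1 to 4 days, whereas Section 5.1.1 says only that scans are read promptly. It also needs an assumption about CSF kinetics that the documents do not supply, and a half-life from single doses of 0.3–10 mg/kg. Section 1.2.5 does report dose-proportional kinetics up to 120 mg/kg Q4W, which makes the half-life a reasonable working value, but not a measured one at this dose.

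There are mitigations. Footnote m requires the actual CSF date and time to be recorded, Section 4.5.7.6 permits an extra serum PK sample at an unscheduled visit, and Section 6.5.3 plans population PK modelling, so serum at the time of the draw could be measured or estimated. The ratio is exploratory and descriptive. These points limit the harm. They do not remove the conflict: the extra sample is optional and not linked to the CSF draw, and Section 6.5.3 plans a tabulated ratio without stating any time matching.

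**Conclusion.** The inconsistency is certain and depends on no assumption about read time. At a Week 53 visit with a dose, puncture first requires at least 3 days from puncture to dose where footnote m allows at most 1. A site that uses that order will either separate CSF from the dosing-day serum sample by at least 3 days plus read time, which is the likelier result, or dose before the MRI is read.

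The reach is narrow: CSF-substudy patients at sites that choose puncture first, at a visit with dosing. The effect on the CSF/serum ratio cannot be fixed from the documents. The serum decline alone is a factor of about 1.08 to 1.13 at the minimum gap, given the 17–26 day half-life, and more with a longer read. It is worth correcting because an order that the protocol permits leads a site into a deviation from either a safety check or a sampling window.

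**What to change.** Reconcile Section 4.5.9 with Appendix 1 footnotes m and s so that every order offered at Week 53 can meet both the CSF window and the MRI rule. As the footnotes stand, only MRI first, of the two orders offered, fits both. Which rule should yield is for the sponsor to decide.

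If puncture first is retained, state the CSF timing that applies under that order and require a serum PK sample at the time of the CSF draw. Section 4.5.7.6 already permits unscheduled PK samples, so this makes an existing option mandatory in one situation. Section 6.5.3 should then say that the ratio uses the serum sample paired with the CSF.

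The cost is about a sentence in Section 4.5.9 and a cross-reference in footnote m, with a line in Section 6.5.3 if puncture first stays. For CSF-substudy patients it means slightly less scheduling freedom, or one extra blood sample.
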